#### **10.14.2.** Clinical Laboratory Evaluations

Descriptive statistics for chemistry and hematology parameters at screening will be summarized for the safety population by treatment arm. Post-baseline laboratory parameters collected as part of AEs or at unscheduled visits will be included in listings.

Listings will be provided by treatment arm. Values for any hematology, chemistry, and serology results that are outside the laboratory reference ranges will be flagged on the individual participant data listings as high or low.

#### **10.14.3.** Clinical Examination of the Back (Injection Site)

Clinical examinations of the back and injection site will be performed regularly during the study. The following examination criteria will be assessed and the proportion of participants with symptoms will be summarized by visit:

- Pain
- Erythema
- Swelling
- Pruritus
- Warmth
- Hematoma
- Induration
- Other skin reactions

Injection site reactions will also be recorded as AEs.

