## 7.1. Participant Inclusion Criteria

Participants are required to meet ALL of the following inclusion criteria:

- 1. Male or female, between 18 and 90 years of age, inclusive.
- 2. Sufficiently severe facet arthropathy of lumbar facets as determined by imaging (e.g., MRI, CT, X-Ray, etc.) to establish an underlying basis of disease, as determined by usual bony and ligamentous signs of osteoarthritis (OA). Use of historical images permitted if obtained within the last 12 months.
- 3. Complaint of nociceptive, mechanical pain of lumbar spine, in particular pain localized to paramedian axis as opposed to midline or radicular. Radicular pain as a secondary finding may be allowed if it is in addition to mechanical pain and can be clinically distinguished by subject
- 4. LBP (Low Back Pain) worsened by activity or motion of region
- 5. Have had a positive diagnostic facet pain block with lidocaine; admittance if subject gains 50% relief of pain within 30 minutes of test injection
- 6. Be free of local or intra-articular infection, tumor or other causes of localized LBP, for example, spondylolysis/pars defect, and adjacent vertebral body compression fracture based on imaging evaluation.
- 7. Symptomatic disease because of osteoarthritis, established by imaging of facet joint and defined as a worst pain of at least 50 at the Screening Visit and the Baseline (Day 0) Visit (based on scale of 0 to 100, with 100 representing "pain as bad as you can imagine") using Visual Analog Scale (VAS).
- 8. Stable analgesic regimen during the 4 weeks prior to enrollment. Participants who are not currently on any analgesics at the time of enrollment because they have discontinued prior analgesic therapy due to intolerance or lack of effect may be included. New analgesics or changes to the pre-established regimen during the study, with the exception of rescue medication use, are not permitted.
- 9. Inadequate pain relief with prior therapies lasting  $\geq 3$  months.
- 10. In the judgment of the Investigator, acceptable general medical condition
- 11. Heterosexually active participants, male and female who are not surgically sterile or postmenopausal, must agree to use effective contraception, including abstinence, for the duration of the study and for 3 months after the study is completed
- 12. Have suitable facet joint anatomy for intra-articular injection
- 13. Willing and able to return for the follow-up (FU) visits

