# 8.2. Investigational Product Administration

Investigational product (XT-150 or placebo) will be administered as two bolus, bilateral intraarticular injections into the facet joint. The injection will be performed with fluoroscopic guidance.

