# 9.2. Baseline (Day-1 or Day 0)

Baseline assessments may be completed the day before or day of study drug administration, before the XT-150 injection.

- Brief physical exam, including examination of the injection site.
- Obtain any changes from the complete medical history.
- Record any changes or updates in medications, including pain medications (prescription and non-prescription) and therapies (e.g., physical therapy, acupuncture) administered since Screening visit.
- Efficacy assessments
  - VAS score. Verify VAS ≥50.
  - Oswestry Disability Index
  - International Physical Activity Questionnaire (IPAQ) short form
  - SF12
  - Record participant's response to the OA question: "Considering all the ways that facet pain, the pain that brought you into this study, affects you, how are you doing today?" on a scale of 1 to 5, 1 being very good (asymptomatic and no limitation of normal activities) to 5, very poor (very severe, intolerable symptoms and inability to carry out normal activities)
- Clinical assessments

- Measure vital signs (temperature and the site collected [oral, rectal, temporal, or tympanic], heart rate, blood pressure, and respiratory rate)
- Laboratory assessments
  - Obtain serum for analysis of IL-10 protein and anti-IL-10 antibodies
  - Obtain whole blood for plasmid DNA analysis
- Confirm participant qualification by inclusion/exclusion criteria. Enroll participant prior to dosing

## 9.3. Day 0

- Before administration of study drug:
  - Confirm that all study criteria are met (inclusion and exclusion)
  - Brief physical exam
  - Injection site examination
  - Record any ongoing medical observations that occurred since Screening visit
  - Record any new AEs since Screening
  - Record any concomitant medications since Screening including prescription, OTC and herbal medications. Ensure no excluded medications.
- Administer study drug (see Section 8 for details on preparation)
  - Aseptic techniques will be used in the preparation and administration of XT-150
  - Injections will be guided by ultrasound, fluoroscopy or equivalent visualization
  - All injections of study drug must be performed by a specialist who is qualified, trained, and experienced to perform intra-articular injections to the Facet joint.
  - Examine injection site for infections or reactions
- Clinical assessments
  - Monitor Participant for approximately for 4 hours for signs of study drug reaction.

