## 10.7.2. Localized Signs of Infection or Inflammation at the Injection Site

Events that, in the opinion of the Investigator, may represent localized signs of infection or inflammation at the XT-150 injection site (e.g., pain, erythema, swelling, pruritus, warmth, hematoma, induration) must be recorded as AEs on the CRF. In general, these events will be temporally related to the injection.

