#### XALUD THERAPEUTICS, INC. Study Drug: XT-150

#### Protocol: XT-150-1-0302 Statistical Analysis Plan, Version 3.0

Scheduled Event	Screen	Baseline a and Dosing	Follow-up				Dosing	Follow-Up					EOS
Study Day	-30 to -1	0	7 (±1)	14 (±1)	30 (±2)	60 (±7)	90 (±7)	120 (±7)	150 (±7)	180 b (±7)	210 (±7)	240 (±7)	270 (±14)
Vital Signs	X	Х	Х	Х	Х	X	X	Х	X	X	X	Х	X
Clinical Exam of the Back (injection site)	X	Х	Х	X	Х	X	X	Х	X	X	X	X	Х
Brief Physical Examination		Х	Х	X	X	X	X	Х	X	X	X	X	X
Record AEs		Х	Х	X	X	X	X	Х	X	X	X	X	X
Record SAEs		Х	Х	X	X	X	X	Х	X	X	X	X	Х
Record Concomitant Medications		Х	Х	Х	Х	X	X	Х	X	X	X	X	Х
Laboratory Assessments													
HIV, Hepatitis B and C	X												
Serum Chemistries	X												
CBC with Differential and Platelet Count	X												
Pregnancy Test (for WOCBP) j	X						X						Х
Whole Blood for Plasmid DNA Biodisposition k		Х	Х	Х	Х								
Serum for IL-10 and Anti-IL-10 Antibody Assessments		Х	Х	Х	X	X	Х			X			Х
Study Drug Administration													
Enroll Participant 		Х											
Administer Study Drug m		Х					X 						

a Baseline assessments are performed before injection on Day 0 OR up to one day before study drug administration. Vital signs also assessed at 1 hour after study drug administration.

b Participants who were enrolled in the study prior to implementation of Protocol Version 3.0 08Jun2022 and either are past their Day 90 visit or do not consent to the Day 90 dose will complete the study at Day180. At this visit, all EOS procedures should be completed.

c Informed consent must be obtained before initiating any study procedures.

d Obtain demographics (age, race, gender) and complete, relevant, medical, and surgical history (including currently active conditions and inactive pain conditions diagnosed) at the Screening visit. Update medical and surgical and pain treatment history at the baseline visit. The physical examination includes the injection site for infections or reactions.

e Record prior medications, including prescription and nonprescription medications and herbal supplements. Update prior medications at the baseline visit.

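### SAP 10.14.3 reports injection-site Pain as plain prevalence with no pre-injection reference, so existing facet pain can dilute, and analgesia can reverse, a true excess of injection-site pain

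*SAP*

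**What the plan says.** SAP 10.14.3 lists eight examination items, with Pain first, and states that "the proportion of participants with symptoms will be summarized by visit". SAP 10.14 makes all safety summaries by treatment arm. In the legible text, 10.14.3 gives no rule for new or worsened findings, no reference to the examination before an injection, and no rule for telling injection-site pain from facet pain. It adds that injection-site reactions are also recorded as adverse events.

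On the population, Protocol 7.1 requires "pain localized to paramedian axis as opposed to midline or radicular" (criterion 3) and symptomatic disease "defined as a worst pain of at least 50 at the Screening Visit and the Baseline (Day 0) Visit" (criterion 7). Protocol 8.2 has the product "administered as two bolus, bilateral intraarticular injections into the facet joint".

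On timing, Protocol 9.2 schedules before dosing a "Brief physical exam, including examination of the injection site". Table 1 marks the back examination at Screening and at every visit from Day 0 to Day 270. Protocol 9.3 and 9.4 describe an examination of the site both before and after the injection on Day 0 and Day 90.

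**The concern.** The examined region is the diseased region, and everyone enters with substantial pain there. If an examiner ticks Pain because the facet joint hurts, the row starts high before any injection. It has little room to rise when an injection causes pain, and it falls whenever pain improves for any reason. An arm with more injection pain and some analgesia could look no worse than placebo, or better.

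Safety and tolerability are the primary objective. Protocol 4.4.2 names minor injection-site reactions as the most common XT-150-related events. Protocol 10.7.1 and SAP 10.14.1 treat Grade 2 reactions as events of special interest, and the protocol names pain among them. The SAP uses a pre-dose reference elsewhere: adverse events that start or worsen after the first dose (10.14.1), change from baseline for vital signs (10.14.4) and shifts for the global assessment (10.13.3).

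**Working it through.** **Inputs.** Arm size is 24 (Protocol 14.1, SAP 5.2). The documents give neither the background prevalence of a ticked Pain item (*b*) nor the injection-pain rates (*r*). Both are assumed below, and a range is shown for *b*. New injection pain is taken as independent of existing pain.

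**1. The plan's own figure.** Protocol 14.1 gives a 95% interval of about 29% to 71% for a 50% rate. The exact interval for 12/24 is 29.1% to 70.9%, so it reproduces. It is not in dispute, but it gives the scale: one arm's proportion near 50% is uncertain by about 21 points either way.

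**2. Dilution.** Observed prevalence = *b* + (1 − *b*) × *r*. With the same *b* in both arms, the difference shown is (1 − *b*) × (*r* active − *r* placebo). For a true excess of 20 points:

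| Assumed *b* | Excess shown | Participants in an arm of 24 |
|---|---|---|
| 0% | 20 points | 24 × 0.20 = 4.8 |
| 50% | 0.50 × 20 = 10 points | 2.4 |
| 80% | 0.20 × 20 = 4 points | 0.96 |
| 90% | 0.10 × 20 = 2 points | 0.48 |
| 100% | 0 points | 0 |

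**3. A larger effect.** Assume reaction rates of 40% active and 5% placebo, a true difference of 35 points. Prevalence shows 70.0% v 52.5% (17.5 points) at *b* = 50%, 88% v 81% (7 points) at 80%, and 97.0% v 95.3% (1.8 points) at 95%. As a yardstick only, since no test is planned here, a two-sided 5% comparison with 24 per arm has power of about 85% for the undiluted difference, and about 23%, 10% and 5% for these three.

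**4. Sign reversal.** Let analgesia lower the active arm's background from 80% to 60%, with reaction rates of 40% and 5%.
- Active: 0.60 + 0.40 × 0.40 = 76%.
- Placebo: 0.80 + 0.20 × 0.05 = 81%.

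The arm with eight times the reaction rate shows 5 points less Pain.

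**5. What a pre-injection reference recovers.** Take *b* = 80% at the reference examination in both arms, and assume that no new facet pain arises in those without it. New Pain then occurs in 0.20 × 0.40 = 8% of the active arm and 0.20 × 0.05 = 1% of placebo. Relief in the other participants no longer cancels it, so the sign is right. With a presence-or-absence item the 35 points still appear as 7 if all 24 are the denominator. Among those free of Pain beforehand the rates are 40% v 5%, but on only 24 × 0.20 = 4.8 participants per arm. Full recovery of the 35 points needs a graded item, so that worsening can be counted.

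**The case against.** The strongest reply is that the item is not facet pain at all. It stands in a list with erythema, swelling, warmth, induration and other skin reactions. Protocol 10.7.2 gives pain as an example of events that "may represent localized signs of infection or inflammation at the XT-150 injection site". Facet pain itself is self-rated separately on the VAS (Protocol 11.1.1). A careful examiner may tick Pain only for a local reaction, and background would then be low. The entry criterion concerns worst pain at two early visits, not an examination finding at later ones. The diagnostic block is unilateral (Protocol 9.1) while study drug is given bilaterally, so the documents do not show that both injected joints hurt.

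All of this stands. A reader might infer that the row simply measures the disease and cannot show an injection-site reaction. The documents do not support that: the form's wording is not given, a background of 90% or 100% is an assumption, and the signal vanishes only at exactly 100%. Pre-dose examinations and a placebo arm also allow a crude comparison.

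A reader might also infer that injection-site safety goes unassessed. It does not. Reactions are recorded as adverse events, tabulated if they start or worsen after the first dose, and reported as special-interest events from Grade 2.

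Two parts of the reply are incomplete. The placebo arm does not correct for analgesia, which is the effect the trial looks for. The adverse event route depends on investigator opinion, while Protocol 10.4.1 bars events related to facet joint osteoarthritis from being recorded as adverse events, and no rule separates the two. The systematic examination is the natural cross-check, and SAP Section 11 drops the general physical-examination summary.

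**Conclusion.** The concern holds as a weakness in one row of a descriptive safety table. The planned rule mixes pre-existing pain, new injection pain and relief, to whatever extent examiners record facet pain under this item. The loss runs from none, if only local reactions are ticked, through half of a true excess at a 50% background and four fifths at 80%, to all of it at 100%. Reversal needs the further assumption of analgesia large enough to outweigh the reactions, as in step 4. The argument bears on Pain and leaves the other seven items untouched. Because adverse event tables give a second view, this is an improvement worth making before the table is read, and it does not show that the safety assessment fails.

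**What to change.** In SAP 10.14.3, at least for Pain, add by arm and visit the number and proportion of participants whose finding is new, or worsened if the item is graded, against the last examination before the most recent injection. That reference is the pre-injection examination of Day 0 or, once a second dose is given, of Day 90. It has to be written out, because the general baseline in SAP 7.1.1 refers only to the first dose. Show the number free of Pain at the reference examination, so that the reader sees how many could register a new finding. Keep the prevalence table as a supplement, and state that Pain prevalence is not an injection-site reaction rate. If the form or its instructions already restrict Pain to local reactions, say so in this section.

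The cost is one extra table, with no new visits. There are two limits. If the form records only presence or absence, worsening must be read from the adverse event tables. If it does not separate the examinations before and after injection on Day 0 and Day 90, only new findings at later visits can be shown. Where both are recorded on the same day, the tie-break in SAP 7.5 keeps the earlier, so the post-injection finding would need its own row to be seen.

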#### 10.14.4. Vital Signs

Systolic and diastolic blood pressures (mmHg), heart rate (bpm), respiratory rate (breaths/minute), and temperature (°C), as well as height, weight, and BMI, will be summarized using descriptive statistics at all scheduled time points. Descriptive statistics of the change from

baseline to each post-baseline time point will also be provided. Abnormal and clinically significant vital signs will be summarized at each timepoint, with abnormal vitals being described in the table below.

Vital Sign	Threshold
Diastolic blood pressure	> 20 mmHg increase from baseline
Systolic blood pressure	≥ 140 mmHg
Heart rate	< 60 beats/min
Heart rate	> 120 beats/min
Temperature	>102.3 F

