# 10.7. Adverse Events of Special Interest

#### 10.7.1. Adverse Events of Noted Interest in IL-10 Protein Trials

Safety will include the following reported IL-10 protein-associated toxicities as defined by CTCAE (v5.0). Systemic levels of XT 150 produced IL-10 protein are expected to be more than 1000-fold lower than when given as a protein solution (Huhn, 1997); and XT-150 will be predominately localized to the facet joint space.

• Grade 1 (unexplained) fever – 38.6°C to 39°C

- Grade 2 allergic, cytokine release, or infusion-related reactions Therapy or infusion interruption indicated but responds promptly to symptomatic treatment (e.g., antihistamines, NSAIDS, narcotics, IV fluids); prophylactic medications indicated for <24 hours
- Grade 2 injection site reaction Pain; lipodystrophy; edema; phlebitis
- Grade 2 neutropenia <1500 to 1000/mm3; <1.5 to 1.0 x109/L

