# 14.4. Safety Analysis

All participants who receive any amount of study drug (Safety Population) will be included in the safety analyses.

[figure not shown]
Safety will be evaluated by presenting summaries of AEs, clinical laboratory tests, and vital signs. Safety variables will be tabulated by treatment group.

[figure not shown]
Adverse events will be graded using the CTCAE v5.0 and will be coded using the Medical Dictionary of Regulatory Affairs (MedDRA®), Version 24 or higher. AEs will be collected for each participant from the signing of the informed consent through the last study visit on Day 180.

A treatment-emergent adverse event (TEAE) is defined as an AE that occurs during or after study drug administration. The incidence of TEAEs will be presented by system organ class (SOC) and preferred term (PT), by SOC, PT, and relationship to the study drug administration, and by SOC, PT, and severity. In addition, the incidence of serious TEAEs and TEAEs leading to discontinuation of study drug will be presented by SOC and PT.

Descriptive statistics for clinical laboratory test results, and vital signs, and for changes from Baseline, will be presented by time point. Baseline is defined as the measurement closest to, but prior to, the administration of study drug. Incidences of potentially clinically significant clinical laboratory results, and vital signs, as defined in the SAP, will also be summarized by time point. A summary of abnormal physical examination findings will also be presented.

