### **5.2.** Sample Size Estimation

Up to 72 participants will be randomized, 24 to each group. The sample size is not based on any formal power calculations.

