#### 10.14.1. Adverse Events

AEs will be coded to system organ class (SOC) and preferred term according to MedDRA, version 24.1. Pretreatment AEs are defined as AEs that have an onset on or after the date the informed consent was signed but before the date of the first dose of study drug. Treatment-emergent adverse events (TEAEs) are defined as AEs that start or worsen after the first dose of study drug. Adverse event severity will be graded using CTCAE v5.0.

Summaries will be provided for TEAEs, with the number and percentage of participants reporting each type of event presented. If a participant reports the same preferred term more than once, it is counted only once within that category. Similarly, if a participant has AEs of two or more preferred terms under the same SOC, then that participant only counts once for that SOC. Furthermore, for a given summary, the preferred term will only be counted once at its worst severity and strongest relationship to study drug.

AEs of special interest will be identified programmatically and reviewed by the study team prior to unblinding. AEs of special interest include:

- (Unexplained) fever
- Grade 2+ allergic, cytokine release, or infusion-related reactions Therapy or infusion interruption indicated but responds promptly to either:
  - symptomatic treatment (e.g., antihistamines, NSAIDS, narcotics, IV fluids)
  - prophylactic medications indicated for  $\leq$ 24 hours
- Grade 2+ injection site reactions
- Grade 2+ neutropenia

The following summaries and listings for AEs will be provided:

- An overall summary table of AEs summarizing the number and percent of participants, in the following categories: any AE, any TEAE, TEAEs by highest severity grade, any TEAEs of special interest, TEAEs by relationship to study drug (related, not related), any serious TEAE, TEAEs leading to drug withdrawal, and TEAEs leading to premature withdrawal from the study, any TEAEs with a fatal outcome
- Incidence of TEAEs by MedDRA SOC and preferred terms
- Incidence of TEAEs by MedDRA SOC, preferred terms, and maximum severity grade
- Incidence of TEAEs by MedDRA SOC, preferred terms, and relationship to study drug.

- Incidence of TEAES of special interest, by SOC, preferred terms, and maximum severity grade.
- Incidence of SAEs by SOC, preferred terms, and maximum severity grade
- Listing of all AEs (with non-treatment-emergent events flagged and AEs of special interest highlighted).
- Listing of all AEs of special interest

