#### Table 5:Abnormal Vital Threshold Values

All vital signs will be displayed in by-participant listings. Clinical interpretations that highlight clinically significant vital signs are included.

Table 6:

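### SAP Table 5 flags temperature only above 102.3 F (39.06 °C), so the abnormal vital-sign count misses the whole 38.6 to 39 °C fever range that the protocol lists as of special interest

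*SAP*

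**What the plan says.** - **Protocol 10.7.1**, under Adverse Events of Special Interest, gives IL-10-associated toxicities to be covered in the safety assessment. The first is "Grade 1 (unexplained) fever – 38.6°C to 39°C".
- **Protocol 14.4** leaves the vital-sign limits to the SAP: "Incidences of potentially clinically significant clinical laboratory results, and vital signs, as defined in the SAP, will also be summarized by time point".
- **SAP 10.14.4** summarizes temperature in °C and then says: "Abnormal and clinically significant vital signs will be summarized at each timepoint, with abnormal vitals being described in the table below". The temperature row of Table 5 is above 102.3 F. There is no lower tier and no change-from-baseline rule for temperature.
- **SAP 10.14.4, text after Table 5**, puts all vital signs in participant listings and adds: "Clinical interpretations that highlight clinically significant vital signs are included".
- **SAP 10.14.1** carries unexplained fever over as an event of special interest, but without the protocol's grade or temperature range. It also says: "AEs of special interest will be identified programmatically and reviewed by the study team prior to unblinding".

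**The concern.** The protocol asks the SAP to say which vital signs count as potentially clinically significant, and elsewhere names a specific temperature range as a toxicity to watch. One would expect the flag to reach that range. Instead the SAP cut-off sits just above its upper end, in a different unit from the rest of the section, and no reason is given.

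Safety is the primary objective. Fever is one of the effects that the protocol anticipates from IL-10 (4.4.4 and 4.4.5). Temperature is measured at every visit (Protocol Table 1) and about 1 hour after each dose (9.3 and 9.4). By contrast, neutropenia, another item in 10.7.1, has no scheduled post-baseline measurement, because SAP Section 11 records that laboratory tests are done at screening only. Temperature is therefore one of the few measured items that bear on that list during follow-up. With the present cut-off, the abnormal-temperature row could read zero in every arm while participants had readings in the range that the protocol singles out.

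**Working it through.** The SAP does not derive 102.3 F from anything, so there is no figure to reproduce. The check is a unit conversion and a comparison of two intervals.

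**Inputs**
- SAP Table 5: abnormal if temperature > 102.3 F (strict inequality).
- Protocol 10.7.1: 38.6 to 39 °C.

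**Formulas:** °C = (F − 32) × 5/9 and F = °C × 9/5 + 32.

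**Conversions**
- Cut-off: (102.3 − 32) × 5/9 = 70.3 × 5/9 = 39.056 °C.
- Lower end of the protocol's range: 38.6 × 9/5 + 32 = 101.48 F.
- Upper end: 39.0 × 9/5 + 32 = 102.20 F.

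**Distances**
- Upper end to cut-off: 39.056 − 39.0 = 0.056 °C, or 102.3 − 102.20 = 0.10 F.
- Lower end to cut-off: 39.056 − 38.6 = 0.456 °C, or 102.3 − 101.48 = 0.82 F.

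**Rule applied to readings**

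| Reading (°C) | In F | In protocol's range | Flagged by Table 5 |
|---|---|---|---|
| 38.6 | 101.48 | yes | no |
| 38.7 | 101.66 | yes | no |
| 38.8 | 101.84 | yes | no |
| 38.9 | 102.02 | yes | no |
| 39.0 | 102.20 | yes | no |
| 39.1 | 102.38 | no | yes |

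In 0.1 °C steps, 0 of 5 readings in the range are flagged. If thermometers read in 0.1 F steps, the readings in the range run from 101.5 F (38.611 °C) to 102.2 F (39.0 °C). That is 8 values, and 0 of 8 are flagged. A grid of 0.0001 °C steps, with or without rounding to 0.1 F, also gives none. The first flagged readings are 39.1 °C and 102.4 F (39.111 °C). A reading of exactly 102.3 F falls under neither definition.

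**Where a reading of, say, 38.8 °C would appear under the current SAP**

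| Output | Shows it? | Count by arm and visit? |
|---|---|---|
| Abnormal vital signs (Table 5) | no | no |
| Clinically significant vital signs (10.14.4) | only if so judged; no numeric rule | of judged readings only |
| Temperature summary with maximum (7.2, 10.14.4) | yes, within the range and up to the maximum | no |
| Participant listings (10.14.4) | yes | no |
| Special-interest event tables (10.14.1) | only if recorded as an adverse event | by arm, of recorded events |

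No planned output counts measured temperatures of 38.6 to 39 °C by arm and visit.

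**The case against.** The strongest reply is that the signal is visible elsewhere, and most of that reply stands. SAP 7.2 includes the maximum in every continuous summary, and 10.14.4 applies this to temperature at each scheduled time point. One participant at 38.6 °C or more at a summarized time point therefore puts that arm's printed maximum at 38.6 °C or higher. The listings show every reading. Unexplained fever is an event of special interest in the SAP with no temperature limit, so a recorded event of any height qualifies. After the early visits, temperature is taken about monthly, and a short fever between visits can enter the data only as an adverse event.

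It is also true that no document requires Table 5 to match the special-interest range. An adverse event definition and an outlier flag may differ, and Protocol 14.4 leaves the choice to the SAP.

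A reader might infer three stronger points, and the documents support none of them.
- **Fevers in the range vanish, so the report would wrongly show no fever.** They do not vanish. Such a statement could be contradicted by the maxima in the same section.
- **No such reading can enter the by-timepoint vital-sign summary at all.** The sentence in 10.14.4 also covers clinically significant vital signs, so an investigator's judgement might bring one in. The exclusion is certain only for the abnormal count.
- **Temperature is the only objective marker of a systemic IL-10 effect.** Protocol Table 1 also schedules serum IL-10 at Baseline and Days 7, 14, 30, 60, 90, 180 and 270.

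What survives the reply is narrower. A maximum does not say how many participants were affected, a listing gives no incidence by arm, and the event tables depend on the fever having been recorded.

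**Conclusion.** The mismatch is exact and depends on neither rounding nor recording unit: 0% of the protocol's 38.6 to 39 °C range can be counted as abnormal under Table 5. It is an unreconciled pair of definitions, compounded by mixed units, and not an arithmetic error. The consequence is limited to one missing tabulation, the count by arm and visit of measured temperatures in that range.

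The conclusion rests on reading Table 5 as the SAP's answer to Protocol 14.4, and on the special-interest search working on recorded adverse events, as its wording implies. It says nothing about how many such readings occurred or which temperature limit is clinically right. This is worth correcting because safety is the primary objective and the correction is cheap. It does not threaten the safety conclusions by itself.

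**What to change.** Reconcile Protocol 10.7.1, SAP 10.14.1 and SAP Table 5:

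1. Add to Table 5, for tabulation only, a temperature tier starting at the protocol's own lower bound (≥38.6 °C), alongside the existing cut-off.
2. State both tiers in °C, the existing one as >39.06 °C, and apply them to unrounded conversions. Otherwise 101.4 F (38.556 °C) rounds up to 38.6 °C and 102.3 F (39.056 °C) rounds up to 39.1 °C, and each would be flagged wrongly.
3. List every flagged reading that has no matching fever adverse event, for the special-interest review that SAP 10.14.1 already places before unblinding.
4. In SAP 10.14.1, say whether unexplained fever is meant to carry the protocol's temperature range.

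The cost is one added table row, one programming condition and one short listing, plus a few more flagged readings. No new data are needed and clinical management does not change. SAP Section 2 provides for an amendment before database lock. After lock, SAP 7.2 would require the added count to be labelled post hoc.

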#### 4.2. Study Endpoints

#### Safety Endpoints:

- Treatment-emergent adverse events (TEAE).
- Treatment-emergent serious adverse events (SAE).
- Abnormal clinical laboratory tests (chemistry and hematology).
- Vital signs (blood pressure, pulse, respiratory rate, and body temperature).
- Physical examination findings.

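### SAP Table 5 has no criterion for low or falling blood pressure or for respiratory rate, and its systolic and low-heart-rate counts mix new with pre-existing values

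*SAP*

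**What the plan says.** Protocol 14.4 leaves the definition of a notable vital sign to the SAP: "Incidences of potentially clinically significant clinical laboratory results, and vital signs, as defined in the SAP, will also be summarized by time point". SAP 10.14.4 supplies it: "Abnormal and clinically significant vital signs will be summarized at each timepoint, with abnormal vitals being described in the table below". Table 5 is the only such definition in the SAP.

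Table 5 has five rules:
- diastolic pressure: "> 20 mmHg increase from baseline";
- systolic pressure: 140 mmHg or more;
- heart rate: below 60 beats/min;
- heart rate: "> 120 beats/min";
- temperature: above 102.3 F.

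The safety endpoints in SAP 4.2 include "Vital signs (blood pressure, pulse, respiratory rate, and body temperature"), so respiratory rate has the same standing as blood pressure. The same SAP section also plans descriptive statistics at scheduled time points, and states that change from "baseline to each post-baseline time point will also be provided". By-participant listings follow, for which the SAP says: "Clinical interpretations that highlight clinically significant vital signs are included".

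**The concern.** Safety and tolerability are the primary objective, and the abnormal-value table is where vital-sign incidence is counted by arm. As written, it covers one direction of blood-pressure change only and leaves out one named vital sign.

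Two features of this trial add weight. First, SAP 10.14.1 lists "Grade 2+ allergic, cytokine release, or infusion-related reactions" among the events of special interest, and Protocol 9.3 and 9.4 schedule vital signs about one hour after each injection as part of the observation for drug reactions. Second, SAP section 11 records that no post-baseline laboratory tests are scheduled and that the physical-examination summary has been dropped. Vital signs therefore carry more of the scheduled systemic safety picture than they otherwise would.

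The second issue is baseline. The diastolic rule is relative to baseline, but the systolic rule and the low-heart-rate rule are absolute. Someone who met either before dosing can be counted as abnormal afterwards with nothing having changed. Ages run from 18 to 90, and no criterion in Protocol 7.1 or 7.2 sets a blood-pressure limit, so some participants may enter above 140 mmHg.

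**Working it through.** The plan states no figure on this point, so there is none to reproduce. The first step is a row-by-row reading of Table 5.

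| Table 5 rule | Can flag low or falling pressure | Covers respiratory rate | Depends on baseline |
|---|---|---|---|
| Diastolic, increase of more than 20 mmHg | No | No | Yes |
| Systolic, 140 mmHg or more | No | No | No |
| Heart rate below 60 | No | No | No |
| Heart rate above 120 | No | No | No |
| Temperature above 102.3 F | No | No | No |

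Result: 0 of 5 rules can flag low pressure, 0 of 5 cover respiratory rate, and 1 of the 2 pressure rules refers to baseline. For example, a systolic pressure of 70 mmHg one hour after injection meets neither pressure rule through that systolic value.

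The second step illustrates the absolute systolic rule. The documents give no mean or SD for systolic pressure, so both are assumed. With a normal distribution and no drug effect, P(systolic ≥ 140) = 1 − Φ((140 − m)/s). The expected count per arm is 24 times that (24 per arm, SAP 5.2).

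| Assumed mean m | Assumed SD s | (140 − m)/s | P(≥ 140) | Expected of 24 |
|---|---|---|---|---|
| 125 | 15 | 1.00 | 15.9% | 3.8 |
| 130 | 15 | 0.67 | 25.2% | 6.1 |
| 135 | 18 | 0.28 | 39.1% | 9.4 |

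A wider set of assumptions gives 4.8% (mean 120, SD 12; 1.1 of 24) to 50% (mean 140; 12 of 24).

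The third step asks how many follow-up flags come from participants already at 140 or above at baseline. Baseline was simulated as m + s·b and follow-up as m + s·(r·b + √(1 − r²)·e), with b and e independent standard normal, no treatment effect, and an assumed visit-to-visit correlation r of 0.5 or 0.7. At mean 130 and SD 15, the share is 49% (r = 0.5) to 60% (r = 0.7). Over means 120 to 140 and SDs 12 to 18 it runs from 23% to 75%. The direction is clear, but the size depends on inputs that the documents do not provide.

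**The case against.** The strongest reply is that nothing is hidden. SAP 7.2 defines continuous summaries to include the minimum and maximum. A systolic value of 70 mmHg could therefore show as a group minimum, and a large fall as the minimum change. It would be in the listings, could be judged clinically significant by a blinded investigator and summarized as such, and could be an adverse event. Special-interest reactions are counted through adverse events, not through Table 5. A reader might infer that the plan cannot show hypotension at all. The documents do not support that.

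What remains is narrower. A minimum shows the most extreme value but not how many participants had a fall. Listings give no incidence. The clinically significant category has no stated criterion, so it does not replace a count against a fixed rule.

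On baseline, randomization against placebo balances pre-existing high readings in expectation, and a summary at each time point may already include the baseline visit. Both points are fair. But balance in expectation is loose at this size. With 25.2% of readings at 140 or above (assumed), the SD of the difference between two arms of 24 is √(2 × 24 × 0.252 × 0.748) ≈ 3.0 participants. A group-level baseline count also does not show whether the same participants are flagged later.

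A reader might also infer that the table is filled by pre-existing hypertension, or that anyone over the limit at entry is counted at every visit. Neither follows. No baseline pressures are given, readings vary between visits, and the diastolic row is already relative to baseline.

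Finally, this is a descriptive table in a study without formal power, and no test or stated decision rule depends on it. That limits the consequence but does not remove the gap.

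**Conclusion.** The point holds in limited form. It follows from the text alone that Table 5 cannot flag a low or falling systolic or diastolic pressure, that it has no respiratory-rate criterion for a named safety endpoint, and that its systolic and low-heart-rate rules do not separate new from pre-existing values. A fall could be seen elsewhere in the outputs but would not be counted under the abnormal-value criteria that Protocol 14.4 leaves to the SAP.

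The systolic counts may be inflated by values present at entry, by an unknown amount. The 16% to 39% range rests wholly on an assumed mean of 125 to 135 and SD of 15 to 18 mmHg, and it describes readings at or above 140, not participants with hypertension at entry. The point is worth correcting because it concerns the primary objective and the data are already collected. It does not show that the safety evaluation as a whole would miss a reaction.

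**What to change.** Amend the SAP before database lock, as SAP section 2 allows.

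1. Add criteria for low or decreasing systolic and diastolic pressure and for respiratory rate to Table 5, or state why they are left out. The sponsor's clinical team should set the numerical limits.
2. State the reference value for any change criterion. SAP 7.1.1 defines baseline as the last value before the first dose. For the one-hour readings, the alternative is the same-day value before that injection. The choice matters at Day 90, where SAP baseline is about three months old. It also matters on Day 0, because Protocol 9.2 lets baseline assessments be done the day before.
3. Report the absolute systolic and heart-rate criteria as treatment-emergent, counting participants who did not meet the criterion at baseline, and show the baseline count or a shift table alongside.

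The cost is a few table rows and the matching program lines, with no new data collection. The downside is a slightly longer table in which a few flags will arise by chance.
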